### 12.7.3 Effect size justification

The effect size was chosen based on recently published data using immunotherapy for mucosal head and neck cancer demonstrating clinical response in approximately 50% of patients.

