## **2.3 Rationale**

Encouraging clinical data emerging in the field of tumor immunotherapy have demonstrated that therapies focused on enhancing T-cell responses against cancer can

result in a significant survival benefit in patients with advanced malignancies (Hodi et al. 2010; Kantoff et al. 2010; Chen et al. 2012).

There are several benefits of a neoadjuvant approach to cSCC. Given the critical location of these lesions and the impact on patients from disfigurement and functional impairment, minimizing tissue resection while not compromising outcomes is an important goal of treatment. Reduction in surgical margins in responders may significantly impact a patient's quality of life and patient reported outcomes.

While the most aggressive cSCCs have been treated with adjuvant chemotherapy, use of immune checkpoint inhibitors may have a distinct advantage for being used in the neoadjuvant setting. Inhibition in the presence of a large tumor mass may theoretically be a more ideal time to prime the system and potentially induce a stronger and broader tumor-specific T-cell response. (O'Donnell) Given the significant recurrence rates and mortality associated with advanced cSCC, future studies could assess if this immune response can increase DFS and may ideally select which patients benefit from further treatment in the adjuvant setting. Neoadjuvant window of opportunity trials also provide a unique opportunity to study biological correlates and markers of response in surgically curable disease.

The experience with neoadjuvant treatment is growing. A study of neoadjuvant nivolumab in untreated, surgically resectable early stage non-small cell lung cancer enrolled 22 patients, of which 20 patients were able to complete the 2 cycles of therapy. (NCT02259621) Among these patients, 45% had a major pathological response, and none of the patients had any treatment-related delays in surgery. 20 of 21 patients were able to undergo complete surgical resection. (Forde)

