A pilot study in cSCC was presented at the 44th European Society of Medical Oncology in 2019 using 2 doses of neoadjuvant cemiplimab for patients with Stage 3 and 4 cSCC of the head and neck. (NCT03565783) In this study of 20 patients, the treatment was well tolerated with no grade 3 or 4 AEs. 55% of patients achieved a pathological complete response and 15% of patients achieve a major pathological response (<10% viable tumor). All patients were able to proceed with anticipated curative surgical resection. (Gross)

In addition to this trial, other studies have shown a neoadjuvant approach is feasible with cutaneous malignancies and can result in decreased surgical defects. Blank et. al. examined neoadjuvant versus adjuvant ipilimumab plus nivolumab in macroscopic stage III melanoma and found that all of the patients in the neoadjuvant treatment arm were able to undergo the anticipated surgery. Of the 9 patients evaluable in the neoadjuvant arm, 78% achieved a significant pathological response and majority had a decrease in lesion size. In a trial of vismodegib used in a neoadjuvant fashion prior to treatment of high-risk basal cell carcinoma, surgical defect size was reduced by 27% in patients who were able to complete 3 months of treatment with all patients able to complete surgical resection. (Ally)

The risks of this trial, similar to other neoadjuvant trials, include the possibility of disease progression resulting in either a more extensive resection than initially anticipated or loss of opportunity for curative surgery. Encouraging data from a preliminary study (NCT03565783, Gross) showed that the risk of this is likely low and worth the potential opportunity to reduce lesion size. This risk will be minimized by careful monitoring of visible lesions following each cycle, and also includes an additional imaging study after the second dose of atezolizumab to check for radiographic evidence of disease progression.

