#### **10.1 Primary and Secondary Outcome measures**

The primary outcome measure for each patient is an indicator for successfully completing 3 cycles of neoadjuvant atezolizumab, followed by surgical resection of remaining disease. The treatment will be evaluated as non-feasible for patients who have disease progression during neoadjuvant treatment, discontinue study medications due to toxicity, or are not able to undergo curative surgical resection after the 3 cycles of treatment.

Patients who decline surgical intervention after completing the neoadjuvant treatment will be considered as having successfully received neoadjuvant treatment.

In this study, feasibility was chosen as the primary endpoint to assess whether patients can successfully complete the neoadjuvant treatment without significant disease progression precluding curative surgical resection, and with acceptable toxicity. Since the patient population will include tumors that are resectable at presentation (and patients will be medically fit to undergo surgery), any postponement of definitive surgical resection will need to demonstrate that this does not adversely affect the opportunity for curative therapy. If this postponement of surgery proves to not cause harm and administration of neoadjuvant treatment is feasible, this study may add an additional cohort to evaluate a combination of immune checkpoint inhibitors in this setting. Future studies can be designed that evaluate additional clinical endpoints.

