### **12. STATISTICAL CONSIDERATIONS**

#### **12.1 Statistical Design**

The primary objective is to determine the feasibility of three doses of atezolizumab prior to surgery in patients with advanced cutaneous squamous cell carcinoma. Our baseline assumption is that 50% of the population will complete all 3 doses of atezolizumab and then proceed to surgery. We can prove that with 20 patients by showing that 85% of the patients enrolled will complete the 3 neoadjuvant cycles of PD-L1 and then proceed to surgery. We will also be collecting demographic and descriptive data on tumor characteristics, and therapies. Please refer to sections 12.4 to 12.7 for the study's statistical plan.

This approach will be considered feasible if 17 or more patients are able to complete neoadjuvant treatment and proceed with surgical resection of disease. If 4 or more patients are unable to complete neoadjuvant treatment due to toxicity or tumor progression, or have unresectable disease at the time of surgery, this approach will be considered unfeasible. Patients who decline immunotherapy or surgery due to reasons not related to toxicity or tumor progression, will not be considered a treatment failure.

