### 12.7.2 Sample size justification

The primary objective is to determine the feasibility of three doses of atezolizumab prior to surgery in patients with advanced cutaneous squamous cell carcinoma. The sample size of evaluable 20 patients allows at least 80% power to reject the null hypothesis of 50% if the true fraction is above 80% (or a difference  $>30\%$ ) using binomial enumeration of all possible outcomes, with a test at the 5% significance level. We expect the true fraction is 85%, which means that we are well powered to detect an effect size that is bigger than 30%.

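### The 50% null rests on a tumour response rate, and the stated 80% power belongs to a 15/20 cutoff, not to the 17/20 rule that decides feasibility

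*Combined protocol and SAP*

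**What the plan says.** The primary outcome in section 10.1 is "an indicator for successfully completing 3 cycles of neoadjuvant atezolizumab, followed by surgical resection of remaining disease". Progression during treatment, discontinuation for toxicity and inability to have curative resection count as failures. Response is a separate, secondary outcome (sections 1.2 and 10.2).

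Section 12.1 sets the benchmark: "Our baseline assumption is that 50% of the population will complete all 3 doses of atezolizumab and then proceed to surgery". Section 12.7.2 then says: "The sample size of evaluable 20 patients allows at least 80% power to reject the null hypothesis of 50" per cent "if the true fraction is above 80" per cent. It uses exact binomial enumeration at the 5% level, does not say whether the test is one- or two-sided, expects a true rate of 85%, and concludes that the study is well powered.

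Section 12.7.3 gives the only justification, which it offers for the effect size: published data "using immunotherapy for mucosal head and neck cancer demonstrating clinical response in approximately 50% of patients".

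The decision rule is in section 12.1: feasible with 17 or more successes, unfeasible with four or more failures. Sections 7.2 and 12.3 stop the study at the fourth failure. Section 12.5 describes the primary analysis as a percentage plus case studies.

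**The concern.** There are two gaps. First, a response rate is not a completion-and-resection rate. A patient with stable disease who receives three doses and is resected is a success here but a non-responder. The figure also comes from a different cancer. In this design 50% appears only as the null, so that null has no relevant support.

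Second, the hypothesis test and power in 12.7.2 belong to a cutoff that the plan never uses. A reader of 12.7.2 would think the study has at least an 80% chance of a positive result at a true 80%, and more at 85%. The result that counts as positive is set elsewhere and is stricter. What is at stake is how the result is read when it feeds into the larger trial in section 12.8: what a pass shows, and how often a regimen performing as expected would fail.

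**Working it through.** **Inputs.** n = 20 evaluable, null 50%, alternative 80%, expected rate 85%, 5% level (12.7.2); feasibility at 17/20 (12.1); stop at four failures (7.2, 12.3). I assume that each of the 20 is classed as success or failure, and that outcomes are independent with a common rate p.

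**Formula.** P(X ≥ r | p) = Σ over k = r..20 of C(20,k) p^k (1−p)^(20−k).

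**1. Reproduce the plan's figure.** At p = 0.50 the denominator is 2^20 = 1,048,576.
- P(X ≥ 14) = 60,460 / 1,048,576 = 0.0577, above 5%.
- P(X ≥ 15) = 21,700 / 1,048,576 = 0.0207, below 5%.

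The critical value is therefore 15/20. It is the same for a one-sided 5%, one-sided 2.5% or two-sided 5% test (two-sided size 2 × 0.0207 = 0.0414), so the missing sidedness does not matter here. Power at 80% is P(X ≥ 15 | 0.80) = 0.804, which matches the plan.

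**2. Apply the declared rule.** At p = 0.50, P(X ≥ 17) = (1,140 + 190 + 20 + 1) / 1,048,576 = 0.0013. The stop at the fourth failure does not change the pass probability, because four failures leave at most 16 successes.

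| True rate | Reject 50% (≥ 15/20) | Declared feasible (≥ 17/20) |
|---|---|---|
| 50% | 2.1% | 0.13% |
| 60% | 12.6% | 1.6% |
| 65% | 24.5% | 4.4% |
| 70% | 41.6% | 10.7% |
| 75% | 61.7% | 22.5% |
| 80% | 80.4% | 41.1% |
| 85% | 93.3% | 64.8% |
| 90% | 98.9% | 86.7% |

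The cutoff equals the expected count (0.85 × 20 = 17), which is why the pass probability at the expected rate is well short of 80%. A result of 15 or 16 rejects 50% yet is declared unfeasible. Its probability is 93.3% − 64.8% = 28.5% at a true 85%, and 80.4% − 41.1% = 39.3% at a true 80%.

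**3. What each result excludes** (Clopper-Pearson limits).
- 15/20: two-sided 95% CI 50.9% to 91.3%.
- 17/20: two-sided 95% CI 62.1% to 96.8%; one-sided 95% lower limit 65.6%. As a one-sided test of 65%, 17/20 has size 4.4%. The two-sided interval still contains 65%.

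**4. Relevant data already cited in section 2.3.**
- Lung study, two cycles: 20/22 completed = 90.9% (exact 95% CI 70.8% to 98.9%); "20 of 21 patients were able to undergo complete surgical resection" = 95.2% (76.2% to 99.9%).
- Cutaneous pilot, two doses, 20 patients: "All patients were able to proceed with anticipated curative surgical resection", so 20/20 (83.2% to 100%).

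These concern completion or resection, as the endpoint does. The figure in 12.7.3 does not.

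**The case against.** **Section 12.7.3 speaks of the effect size, not the null.** True. But 50% enters the design only as the null, so the link is the natural reading. If it is wrong, the null has no justification at all.

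**Rejecting 50% does not decide feasibility.** This stands. The operative rule is 17/20, with treatment failures reviewed before each further accrual. A reader might infer that the trial could endorse a regimen costing 30–40% of resectable patients their curative surgery. The documents do not support that. At true success rates of 60%, 65% and 70% the rule passes only 1.6%, 4.4% and 10.7% of the time. In addition, a toxicity discontinuation counts as a failure even if curative surgery then goes ahead, so the failure rate is not the rate of lost surgery.

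**The cited studies do not show that 50% is wrong.** This also stands. A null is the rate regarded as unacceptable, and high expected rates bear first on the alternative, already set at 85%. Both studies gave two doses rather than three. The lung completion and resection figures have different denominators and no joint rate, and the pilot text gives resection but not dosing completion. They can inform a floor but do not fix one.

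**A 65% null would be back-calculated from the cutoff.** Correct. It holds only one-sided and follows from none of the data in 2.3. It describes what 17/20 excludes and should not be presented as the justified minimum.

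**Conclusion.** The concern holds as a fault in the stated rationale and power. The response rate in 12.7.3 does not bear on the primary endpoint, and the 50% null has no other support. The arithmetic in 12.7.2 is right for 15/20 but does not describe the decision. At the true 80% named there, the probability of declaring feasibility is 41%, about half the stated figure. At the expected 85% it is 65%, so a regimen performing as expected would miss the rule about one time in three (35.2%).

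The declared rule is much stricter than the null suggests (false-positive rate 0.0013 at 50%), so the error makes the study look better powered than it is and does not make a wrong pass likely. Patient harm is not demonstrated. These figures assume 20 patients each classed as success or failure, and a common success rate.

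**What to change.** Keep 20 patients, the 17/20 rule and the existing stop.

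1. In 12.7.3, remove the response-rate justification. Explain the lowest acceptable rate in terms of completion and resection, citing section 2.3 and noting that those studies gave two doses.
2. In 12.7.2, replace the power statement with the operating characteristics of 17/20: 41%, 65% and 87% at true rates of 80%, 85% and 90%, and 10.7% at 70%. Drop the claim of being well powered.
3. In 12.1 and 12.7.2, state what 17/20 excludes: two-sided 95% CI 62.1% to 96.8%; one-sided lower limit 65.6%, equivalent to a one-sided 4.4% test of 65%. The sponsor should confirm whether that is the intended minimum, and should state the sidedness.

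The cost is wording only, and the stated power becomes less favourable. If the sponsor instead wanted 80% power at a true 85% (one-sided 5%, exact), an assumed floor of 65% would need 31 patients and one of 70% would need 49. Those floors are illustrations and not figures from the documents, and this change is not needed to correct the text.

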## 12.8 Criteria for future studies

If we meet the endpoint for determining that this approach is feasible, we will move towards designing a larger trial that examines surgical margin reduction, disease recurrence rates, and optimal adjuvant therapy strategies. We may also test the feasibility of this strategy using different combination regimens in the future to further increase response rate and tumor volume reduction.

## APPENDICES

### APPENDIX A: Participant Eligibility Checklist

#### I. Subject Eligibility Checklist

A Participant Eligibility Checklist must be completed in its entirety for each subject prior to registration. The completed, signed, and dated checklist must be retained in the patient's study file and the study's Regulatory Binder.

The study coordinator, treating physician and an independent reviewer must verify that the participant's eligibility is accurate, complete, and legible in source records. A description of the eligibility verification process should be included in the EPIC or other Electronic Medical Record progress note.

Protocol Title:	NEOADJUVANT ATEZOLIZUMAB IN SURGICALLY RESECTABLE ADVANCED CUTANEOUS SQUAMOUS CELL CARCINOMA
Protocol Number:	ENT0082 / IRB-59070
Principal Investigator:	[name]

#### II. Subject Information:

Subject Name/ID:
Gender:  Male  Female

#### III. Study Information:

SRC Approved  IRB Approved  Contract signed

#### IV. Inclusion/Exclusion Criteria

Inclusion/Exclusion Criteria			
Inclusion Criteria (From IRB approved protocol)	Yes	No	Supporting Documentation*
1. Signed Informed Consent Form			
2. Age $\geq$ 18 years at time of signing Informed Consent Form			
3. Histologically or cytologically confirmed squamous cell carcinoma			
4. Measurable disease per RECIST v1.1 

• Note that protocol specified imaging is not necessary to fulfill this criterion. For example, a patient presenting with a visible 4cm primary lesion who has obviously RECIST evaluable disease may be considered eligible prior to baseline imaging stipulated in the protocol.

			
5. Availability of a representative tumor specimen that is suitable for determination of PD-L1 immunohistochemical stain evaluation.			
6. ECOG Performance Status of 0 or 1			

Inclusion/Exclusion Criteria			
Inclusion Criteria (From IRB approved protocol)	Yes	No	Supporting Documentation*
7. Adequate hematologic and end-organ function appropriate for surgery as determined by routine preoperative evaluation. If liver function, renal function and hematologic laboratory test results are within limits acceptable for elective surgery. Laboratory results that will need to be obtained within 28 days prior to initiation of study treatment: 
 
AST, ALT, total bilirubin, and alkaline phosphatase (ALP) ≤ 2.5 x upper limit of normal (ULN.).
 
TSH < 13 
 
Patients with a history of a high TSH who are receiving levothyroxine replacement at the time of eligibility evaluation and have no clinical evidence of hypothyroidism are eligible.
 
 
 
			
8. For patients receiving therapeutic anticoagulation: stable anticoagulant regimen			
9. Negative hepatitis B surface antigen (HBsAg) test at screening			
10. For women of childbearing potential: agreement to remain abstinent (refrain from heterosexual intercourse) or use contraceptive methods, as defined below: Women must remain abstinent or use contraceptive methods with a failure rate of < 1% per year during the treatment period and for 5 months after the final dose of atezolizumab. A woman is considered to be of childbearing potential if she is postmenarchal, has not reached a postmenopausal state ( $\geq 12$ continuous months of amenorrhea with no identified cause other than menopause), and has not undergone surgical sterilization (removal of ovaries and/or uterus). The definition of childbearing potential may be adapted for alignment with local guidelines or requirements. Examples of contraceptive methods with a failure rate of < 1% per year include bilateral tubal ligation, male sterilization, hormonal contraceptives that inhibit ovulation, hormone-releasing intrauterine devices, and copper intrauterine devices. The reliability of sexual abstinence should be evaluated in relation to the duration of the clinical trial and the preferred and usual lifestyle of the patient. Periodic abstinence (e.g., calendar, ovulation, symptothermal, or postovulation)			
11. For men: Agreement to remain abstinent (refrain from heterosexual intercourse) or use a condom, and agreement to refrain from donating sperm, as defined below: With a female partner of childbearing potential or pregnant female partner, men must agree to remain abstinent or use a condom during the treatment period and for 5 months after the final dose of atezolizumab to avoid exposing the embryo. Men must agree to refrain from donating sperm during this same period			

## Inclusion/Exclusion Criteria

Exclusion Criteria (From IRB approved protocol)	Yes	No	Supporting Documentation*
1. Patients not eligible for standard of care surgical resection			
2. Distant metastatic disease			
3. Uncontrolled pleural effusion, pericardial effusion, or ascites requiring recurrent drainage procedures (once monthly or more frequently) 
 
• Patients with indwelling catheters (e.g., PleurX®) are allowed.
 
			
4. Uncontrolled or symptomatic hypercalcemia (ionized calcium > 1.5 mmol/L, calcium > 12 mg/dL or corrected serum calcium > ULN)			
5. Active or history of autoimmune disease or immune deficiency, including, but not limited to, myasthenia gravis, myositis, autoimmune hepatitis, systemic lupus erythematosus, rheumatoid arthritis, inflammatory bowel disease, antiphospholipid antibody syndrome, Wegener granulomatosis, Sjögren syndrome, Guillain-Barré syndrome, or multiple sclerosis (see Appendix G for a more comprehensive list of autoimmune diseases and immune deficiencies), with the following exceptions: 
 
• Patients with a history of autoimmune-related hypothyroidism who are on thyroid-replacement hormone are eligible for the study.
 
• Patients with controlled Type 1 diabetes mellitus who are on an insulin regimen are eligible for the study.
 
• Patients with eczema, psoriasis, lichen simplex chronicus, or vitiligo with dermatologic manifestations only (e.g., patients with psoriatic arthritis are excluded) are eligible for the study provided all of following conditions are met:               
 
◦ Rash must cover < 10% of body surface area
 
◦ Disease is well controlled at baseline and requires only low-potency topical corticosteroids
 
◦ No occurrence of acute exacerbations of the underlying condition requiring psoralen plus ultraviolet A radiation, methotrexate, retinoids, biologic agents, oral calcineurin inhibitors, or high-potency oral corticosteroids within the previous 12 months
 
 
 
			
6. History of idiopathic pulmonary fibrosis, organizing pneumonia (e.g., bronchiolitis obliterans), drug-induced pneumonitis, or idiopathic pneumonitis, or evidence of active pneumonitis on screening chest computed tomography (CT) scan 
 
• History of radiation pneumonitis in the radiation field (fibrosis) is permitted.
 
			
7. Active tuberculosis. Patients do NOT have to be screened for tuberculosis for this trial.			
8. Significant cardiovascular disease (such as New York Heart Association Class II or greater cardiac disease, myocardial infarction, or cerebrovascular accident) within 3 months prior to initiation of study treatment, unstable arrhythmia, or unstable angina			

## Inclusion/Exclusion Criteria

Exclusion Criteria (From IRB approved protocol)	Yes	No	Supporting Documentation*
9. Severe infection within 4 weeks prior to initiation of study treatment, including, but not limited to, hospitalization for complications of infection, bacteremia, or severe pneumonia			
10. Treatment with therapeutic oral or IV antibiotics within 2 weeks prior to initiation of study treatment 
 
• Patients receiving prophylactic antibiotics (e.g., to prevent a urinary tract infection or chronic obstructive pulmonary disease exacerbation) are eligible for the study.
 
			
11. Prior allogeneic stem cell or solid organ transplantation			
12. Any other disease, metabolic dysfunction, physical examination finding, or clinical laboratory finding that contraindicates the use of an investigational drug, may affect the interpretation of the results, or may render the patient at high risk from treatment complications			
13. Treatment with a live, attenuated vaccine within 4 weeks prior to initiation of study treatment, or anticipation of need for such a vaccine during atezolizumab treatment or within 5 months after the final dose of atezolizumab			
14. Current treatment with anti-viral therapy for HBV			
15. Treatment with investigational therapy within 28 days prior to initiation of study treatment			
16. Prior treatment with CD137 agonists or immune checkpoint blockade therapies, including anti-CTLA-4, anti-PD-1, and anti-PD-L1 therapeutic antibodies			
17. Treatment with systemic immunostimulatory agents (including, but not limited to, interferon and interleukin 2 [IL-2]) within 4 weeks or 5 half-lives of the drug (whichever is longer) prior to initiation of study treatment			
18. Treatment with systemic immunosuppressive medication (including, but not limited to, corticosteroids, cyclophosphamide, azathioprine, methotrexate, thalidomide, and anti-TNF- $\alpha$ agents) within 2 weeks prior to initiation of study treatment, or anticipation of need for systemic immunosuppressive medication during study treatment, with the following exceptions: 
 
• Patients who received acute, low-dose systemic immunosuppressant medication or a one-time pulse dose of systemic immunosuppressant medication (e.g., 48 hours of corticosteroids for a contrast allergy) are eligible for the study has been obtained.
 
• Patients who received mineralocorticoids (e.g., fludrocortisone), corticosteroids for chronic obstructive pulmonary disease (COPD) or asthma, or low-dose corticosteroids for orthostatic hypotension or adrenal insufficiency are eligible for the study.
 
			
19. History of severe allergic anaphylactic reactions to chimeric or humanized antibodies or fusion proteins			
20. Known hypersensitivity to Chinese hamster ovary cell products or to any component of the atezolizumab formulation			
21. Pregnancy or breastfeeding, or intention of becoming pregnant during study treatment or within 5 months after the final dose of study treatment			

